### Introduction:

Oral health is a vital component of overall health and an important part of a child's well-being (Sharma, Saxena et al. 2021). According to World Health Organization (WHO), oral health is the state of the mouth, teeth and orofacial structures that enables individuals to perform essential functions such as eating, breathing and speaking (WHO 2023). It has been accurately declared that there is no health without good oral health (FDI 2017). The maintenance of oral health plays a crucial role in enabling people to actively engage in societal activities and fulfill their own capacities (WHO 2023). A fundamental aspect of preserving good oral health is recognizing the importance of adhering to appropriate oral hygiene practices (Malik, Sabharwal et al. 2017). To maintain optimal oral health, the Centers for Disease Control and Prevention (CDC) advise fluoridated water, fluoride toothpaste, twice-daily brushing, regular flossing, and yearly dental examinations (CDC 2023). It is well acknowledged that developing good oral hygiene practices from an early age is essential to achieving favorable long-term results (K, Deshpande et al. 2022). Despite significant progress in the field of oral and dental health across several nations, the prevalence of oral health issues remains a persistent worldwide concern (Hashemi, Khorsandi et al. 2021). ). Oral disease encompasses a wide variety of conditions, such as dental caries, periodontal disease, oral cancers, dental erosion, and dental fluorosis. Among these several oral diseases, dental caries and gingival disease are the most prevalent chronic oral conditions in children (CDC 2022) (de Silva, Hegde et al. 2016). Hence, dental caries is a worldwide health issue (Mallineni, Alassaf et al. 2023). It is a relatively common global condition that affects over 621 million children worldwide (Alayadi, Alsiwat et al. 2023). Besides, it has a significant effect on both health and the economy around the world (Innes, Clarkson et al. 2020, Mallineni, Alassaf et al. 2023). Dental caries is a microbiological disease that affects teeth through the process of demineralization and destruction of the inorganic and organic components of dental hard tissue (Mallineni, Alassaf et al. 2023). It may occur in teeth at an early age, and if left untreated, it might lead to potentially serious complications (Gerreth, Ari et al. 2020). Children who have dental caries can experience pain that may negatively impact an individual's ability to eat and maintain proper nutrition, speak clearly, sleep soundly, concentrate effectively, and learn efficiently (Alayadi, Alsiwat et al. 2023). The overall well-being and quality of life of children may also be impacted by dental caries, potentially affecting their school attendance and their performance in the classroom (Alayadi, Alsiwat et al. 2023). It was reported that over 51 million hours of school are

missed per year as a consequence of dental-related illnesses (Kashyap, Reddy et al. 2022). Dental caries influenced by a variety of factors, including biological, behavioral, psychosocial, and environmental factors (Machiulskiene, Campus et al. 2020). Consequently, dietary and hygiene practices, bacterial flora, saliva composition and flow rate, oral health care access, and socioeconomic level all play important role in caries development (Gerreth, Ari et al. 2020). Despite the preventability of dental caries, its prevalence remains significantly high (Adam, Al-Sharif et al. 2022). As stated by WHO, globally 514 million children suffer from caries of primary teeth. This means that the average rate of cases is expected to be 43% (WHO, Global oral health status report 2022). Furthermore, the rate of dental caries among the Arab population ranges from 77% in Jordan to 99.4% in the United Arab Emirates (Al Suwyed, Al Zoman et al. 2021). However, the Saudi Ministry of Health reported that the percentage of tooth decay among children in Saudi Arabia reached 96% (MOH, 2021). Unfortunately, the treatment of dental caries typically involves surgical procedures and restorative therapy, which may induce stress for a child and incur financial burden on the family (Gerreth, Ari et al. 2020). The burden of oral illness keeps rising, and it is particularly serious in low- and middle-income nations. In most high-income countries, oral diseases rank as the fourth most expensive condition to treat. Moreover, the expense of providing curative therapy for dental caries alone in children would reach the overall healthcare budget in most low-income nations (de Silva, Hegde et al. 2016). This might imply that society faces a significant expense as a consequence of a lack of awareness about prevention and an inadequate care supply (Wang, Liu et al. 2022). Therefore, prevention of dental caries in children is widely recognized as a crucial objective since it is usually more cost-effective in comparison to treatment (Wang, Petersen et al. 2018). While it is possible to prevent oral diseases in the initial stages, there is a lack of awareness among many children and their guardians, such as parents and teachers, about the effectiveness of simple self-administered oral hygiene practices in preventing these diseases. Furthermore, policymakers may also overlook this issue. Therefore, the prevention has established as a fundamental principle in current dental healthcare (Gurav, Shetty et al. 2022). Prevention of caries need a comprehensive and collaborative strategy that includes several factors and involves multiple agencies. This approach requires providing health education and promoting the development of life skills (Aljafari, Gallagher et al. 2017). The World Health Organization's (WHO) Ottawa Charter commands the integration of health education into health promotion activities, as the acquisition of knowledge remains a critical component for encouraging behavioral

changes (Aljafari, ElKarmi et al. 2022). Health promotion is provided to help individuals manage and enhance their health. Besides, Oral Health Education (OHE) is an important element of oral health promotion and a necessary component of oral health care. Through educational approaches, information is given to increase oral health awareness in order to adopt a healthy lifestyle, improved attitudes, and desired behaviors (Gurav, Shetty et al. 2022). However, waiting to educate children about oral health until they seek dental care is occasionally too late, especially in nations and communities where people only visit the dentist when experiencing pain. Accordingly, it is important to provide oral health education in nonclinical settings (Aljafari, ElKarmi et al. 2022). Oral health education encompasses several strategies, such as public awareness campaigns, informative presentations in primary schools, the use of oral health films, and establishing a complete and reinforced course that is incorporated into the school curriculum (Gurav, Shetty et al. 2022). The implementation of OHE programs in schools is critical for achieving adaptive changes and improving oral wellbeing. School plays an important part in a child's development, enabling them to proceed towards becoming successful (K, Deshpande et al. 2022). Additionally, school years are a child's physical and mental formative years, shaping them into potential adults. The health behaviors that are developed during this phase will persist until adulthood, old age, and maybe into the next generation (Malik, Sabharwal et al. 2017). Also, children have a rapid capacity for assimilating new information. Furthermore, the acquisition of habits at an earlier stage has a more enduring influence (Sharma, Saxena et al. 2021, Gurav, Shetty et al. 2022). Fortunately, school is one of the most accessible avenues for reaching out to children and their families and considered an ideal platform for providing OHE. They may reach over one billion children worldwide, which supply an excellent opportunity for supporting children to improve their healthrelated behaviors (PEREIRA and MATHEW 2020, Gurav, Shetty et al. 2022). Dental health education in schools is conducted through a variety of methods, from simple educational presentations to technology-enabled multimedia programs that include strategies designed to support behavioral and psychological changes. The efficacy of oral health education in schools is based on the extent to which the acquired health behaviors are retained. In order to have a longlasting effect, it is essential to use repetition and reinforcement approaches in health education (PEREIRA and MATHEW 2020). Studies show that the use of conventional OHE alone does not provide sufficient outcomes for modifying oral health behavior and attitude (K, Deshpande et al. 2022). Furthermore, research has revealed that these particular programs have little impact on oral

hygiene practices and minimal effect on the overall oral health status of children (Malik, Sabharwal et al. 2017, Sharma, Saxena et al. 2021). Nevertheless, conventional methods of education for schoolchildren are still in use (PEREIRA and MATHEW 2020). Education is a three-part process that involves the transmission of knowledge, the development of skills and interests, and the establishment of attitudes and life values (K, Deshpande et al. 2022). It should be delivered in a manner that stimulates the recipient's thoughts rather than just filling their minds with information. Hence, the integration of entertainment with education provides an enjoyable learning experience (K, Deshpande et al. 2022). Moreover, employing interesting approaches to oral health education in schools might help in improvement of children's oral health (Kashyap, Reddy et al. 2022). The use of interactive learning methods offers several benefits, including enhanced attention span, improved memory recall, increased visual alertness, and support for memory strategies and reasoning skills (Sharma, Saxena et al. 2021). Implementation of games as a way of learning has emerged as an interactive learning strategy that has shown promising outcomes. This strategy emphasizes experiential learning as a method of obtaining knowledge (Kashyap, Reddy et al. 2022). Moreover, game-based approach is an effective teaching method that strengthens and expands a child's knowledge base in an attractive and dynamic setting (Sharma, Saxena et al. 2021). Additionally, it has been estimated that children spend nine and a half hour a week playing games. The use of games in education have the capability to activate pre-existing information and act as a motivator for individuals to alter their behavior (Aljafari, Gallagher et al. 2017). While playing games, children happily get valuable experiences and proactively pick up new information without feeling any pressure (Hashemi, Khorsandi et al. 2021). Furthermore, gaming is quite popular, especially among the younger generation (Aljafari, Rice et al. 2015). Currently, such innovative and creative prevention techniques are now being developed in response to the urgent need to tackle the nation's rising prevalence of oral health issues (Kashyap, Reddy et al. 2022). However, the previously stated evaluations have shown that, although these games have the potential to enhance health outcomes, the vast majority of research are of low quality. As a consequence, more comprehensive randomized controlled trials in this field are urgently needed (Aljafari, Rice et al. 2015).

# Study aim and objectives:

#### Aim:

-To evaluate the effect of conventional versus non-conventional oral health education on the oral hygiene status of preschool children and on mothers' oral hygiene knowledge, attitudes, and practices towards their children in Al-Ahsa region.

#### **Objectives:**

-To measure the oral hygiene status of preschool children using simplified oral hygiene index.

-To assess mothers' oral hygiene knowledge, attitudes, and practices towards their children using an online questionnaire.

-To measure the impact of conventional oral health education on the oral hygiene status of preschool children and mothers' knowledge, attitudes and practices.

-To measure the impact of non-conventional oral health education on the oral hygiene status of preschool children and mothers' knowledge, attitudes and practices.

-To compare the effect of conventional versus non-conventional oral health education on the oral hygiene status of preschool children and on mothers' oral hygiene knowledge, attitudes, and practices towards their children.

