# Materials and methods:

**Type of study:** The study will be carried out as a double arm single-blinded randomized controlled trial.

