#### **Exclusion criteria:**

-Special needs kindergartens.

-Illiterate mothers.

-Children with dental anomalies.

-Children with orthodontics appliance.

-Children with systemic diseases (Diabetes mellitus, Hemophilia,

Cancer, Craniofacial anomalies and syndromes).

To avoid deprivation of learning, all children will get oral health education, but they will not be counted in the study sample. Exclusion will occur during the data analysis process.

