#### -At the children level:

Using a computerized random number generator.

Classes will be randomly allocated into the two study groups (conventional and nonconventional) using a a coin toss.

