### In conventional group:

1- A power point presentation will be provided to the children. (One visit)

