### In non-conventional group:

1- Children will be subjected to an interactive learning approach that includes: (Four visits)

-Brain-based learning strategies using storytelling and hands-on activities.

-An online game-based learning platform (Kahoot).

(It can be accessed via a web browser or the Kahoot app).

2-Mothers will be subjected to an oral health education lecture.

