#### Data analysis

Descriptive statistics will be used to summarize baseline characteristics. Inferential statistics, including t-tests for continuous variables and Chi-squared tests for categorical variables, will be used to compare outcomes between the two groups. A significance level of p < 0.05 will be used for all analyses.

Children's oral hygiene status, mothers' knowledge, attitudes, and practices will be the dependent variables in this study. Conventional and non-conventional oral health education will be the independent variables.

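### Objectives 3 and 4 ask for the separate impact of each education programme, but with no uneducated or delayed arm a within-arm change cannot be attributed to either programme

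*Protocol*

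**What the plan says.** The Objectives section lists five aims. The third is "To measure the impact of conventional oral health education on the oral hygiene status of preschool children" and on mothers' knowledge, attitudes and practices. The fourth is "To measure the impact of non-conventional oral health education on the oral hygiene status of preschool children" and on the same maternal outcomes. The fifth is the comparison of the two programmes, so the third and fourth must mean something other than that contrast.

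The design is stated under Materials and methods: "The study will be carried out as a double arm single-blinded randomized controlled trial". The sampling section allocates classes by coin toss to conventional or non-conventional education and names no other group. Children in the conventional group receive one visit with a slide presentation. Those in the non-conventional group receive four interactive visits, followed by weekly online play for 3 months.

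Under Measurements, children's plaque scores and mothers' questionnaires are recorded before the intervention and after 3 months in both groups. The Null Hypothesis and the comparison statement that follows Measurements are both between groups. Data analysis names t-tests and Chi-squared tests that "will be used to compare outcomes between the two groups".

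The mothers' lecture appears in two places. The section on who delivers the programme describes it, in person or online, without naming an arm. The non-conventional group's list includes it, and the conventional group's list does not.

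**The concern.** The word impact in objectives 3 and 4 is causal. To learn what a programme does by itself, one must know what would have happened over the same 3 months without it, and no arm supplies that. The only quantity available for either objective is the before-after change inside one arm.

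The protocol itself shows several reasons why such a change could occur without any education effect:

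- Children aged 5–6 are 3 months older at the second examination, at a different point of the school year.
- They have already been examined once, and Measurement errors mentions a disclosing agent, which makes plaque visible.
- Mothers complete the same questionnaire twice.
- Incentives are offered to keep families in the study.
- An arm that starts high or low by chance will tend to regress towards the mean.

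If the objectives stay as worded, two of the five invite a conclusion that the design cannot support. The drift could also run towards worse plaque, in which case it would hide a real benefit.

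**Working it through.** **What the design identifies.** Let e_C and e_N be the effects of conventional and non-conventional education against no education. Let t be the 3-month change that would occur without education, taken as common to both arms in expectation because classes are randomised.

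- Change in the conventional arm = e_C + t
- Change in the non-conventional arm = e_N + t
- Difference between arms = e_N − e_C

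There are two observable changes and three unknowns. Only e_N − e_C can be recovered, and that is objective 5. Objectives 3 and 4 ask for e_C and e_N, each of which is tied to t. A further test on the same data cannot separate them.

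For example, assume e_C = 0 and e_N = 0.2 SD:

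| Drift t (SD) | Conventional change | Non-conventional change | Difference |
|---|---|---|---|
| 0 | 0 | 0.2 | 0.2 |
| 0.1 | 0.1 | 0.3 | 0.2 |
| 0.2 | 0.2 | 0.4 | 0.2 |
| 0.3 | 0.3 | 0.5 | 0.2 |

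**Sample size used.** The protocol gives 788 pairs before the dropout allowance, so 788 / 2 = 394 per arm. With the allowance, 788 + 78 = 866 and 866 / 2 = 433 per arm. The point disputes none of these figures.

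**Precision of a within-arm change.** In SD units, with before-after correlation r, SE = sqrt(2(1 − r)/n) and the 95% half-width is 1.96 × SE. The protocol gives no r, so a range is shown, and clustering is ignored. At n = 394:

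| r | SE | Half-width |
|---|---|---|
| 0.3 | 0.0596 | 0.117 |
| 0.5 | 0.0504 | 0.099 |
| 0.7 | 0.0390 | 0.076 |

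The change is therefore estimable, and fairly precisely. The difficulty is what it means.

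**How easily drift alone would look like an effect.** The probability that a paired test is significant at two-sided 0.05 when education does nothing is approximately Φ(t/SE − 1.96). At t = 0.1 SD and n = 394:

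- r = 0.3: 0.1/0.0596 = 1.68, and Φ(−0.28) = 0.39
- r = 0.5: 0.1/0.0504 = 1.98, and Φ(0.02) = 0.51
- r = 0.7: 0.1/0.0390 = 2.56, and Φ(0.60) = 0.73

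At t = 0.2 SD and r = 0.5, z = 3.97 and Φ(2.01) = 0.98. The drift sizes are assumptions, and the protocol names no such paired test. Allowing for class clustering would normally widen the SE and lower these probabilities, but it would leave t in the estimate.

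**Mothers.** Set side by side, the conventional list gives no maternal component, the non-conventional list gives a lecture, and the delivery section gives a lecture for mothers of unspecified arm. On the first reading, objective 3 asks for the maternal impact of a programme with no listed maternal component. On another, both arms' mothers are taught. The text does not settle which applies.

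**The case against.** The best reply is that the confirmatory question is already between-arm. The Aim, Hypothesis, Null Hypothesis, comparison statement and Data analysis all point that way, and no hypothesis claims that either programme works by itself. Objectives 3 and 4 may have been meant descriptively. That stands, and it limits the point to the wording of two objectives and what may be concluded from them.

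A reader might go further and infer several things that the document does not support:

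- **That neither quantity can be estimated.** Measurements collects baseline and 3-month data in both groups, so the change within each arm can be estimated. What is missing is attribution.
- **That the lack of a paired analysis is itself a fault.** Data analysis introduces its tests as examples, and a within-arm analysis could sit in a statistical analysis plan that is not at hand. Such a plan could add a test, but it could not add the missing comparator.
- **That the trial will report uncontrolled changes as proof.** Data analysis, followed as written, yields no within-arm result. The risk lies in the objective's wording and is not a stated intention.
- **That the statement "all children will get oral health education" shows there is no control group.** It stands under Exclusion criteria and concerns children not counted in the sample. The allocation and the two group descriptions carry the point without it.

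The protocol also takes one precaution against observation effects: children are not told the examination day. That helps against preparation for the examination, but it does not remove the effect of having been examined before.

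**Conclusion.** The point holds in limited form. Objectives 3 and 4 ask for the impact of each programme separately, and a design with two education arms and no uneducated or delayed comparator cannot attribute a within-arm change to either. This follows from the design and needs no numerical assumption. Objective 5 is unaffected by any drift common to both arms.

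The size can only be illustrated. The 39%, 51% and 73% figures rest on an assumed 0.1 SD drift, correlations of 0.3, 0.5 and 0.7, 394 per arm, no clustering and a test that the protocol does not name. They show that modest drift could pass for an effect, and they do not predict that it will.

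For maternal outcomes, the impact of the conventional programme has no clear meaning until the sections on the mothers' lecture agree.

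**What to change.** - Reword objectives 3 and 4 as: *to describe the change from baseline to 3 months within each group*.
- Report the mean change in each arm with a confidence interval that allows for class clustering, and make no causal claim from it.
- Add one sentence to Data analysis stating that conclusions on effectiveness rest only on the randomised between-arm comparison.
- Reconcile the section on programme delivery with the two group descriptions, so that it is clear which mothers are offered the lecture.

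Arms, sample size and measurements stay as they are. The cost is a few lines of text and giving up the claim that either programme has an impact by itself.

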# **Hypothesis**

Non-conventional oral health education can improve the oral hygiene status of preschool children, and mothers' oral hygiene knowledge, attitudes, and practices towards their children more than the conventional programs.

### **Null Hypothesis**

There is no difference between conventional and non-conventional oral health education on oral hygiene status of preschool children, and on mothers' oral hygiene knowledge, attitude, and practices towards their children.

# Materials and methods:

**Type of study:** The study will be carried out as a double arm single-blinded randomized controlled trial.

### Study area:

The study will be conducted in public and private kindergartens (KG) in Al-Ahsa region, Saudi Arabia, during the period from October 2024 to August 2025.

There are 154 kindergartens distributed among three educational offices: Al-Mubarraz, Al-Hofuf, and Villages Education Offices. This study sampling population will only cover 148 kindergartens since six of schools are excluded as they serve children with special needs.

